1. PROTOCOL SUMMARY

Background: The HEARTS Technical Package was developed by the World Health Organization to address the implementation gap of cardiometabolic care in low- and middle-income countries. Guatemala is a middle-income country that is currently implementing HEARTS. National authorities are interested in exploring how hypertension and diabetes management can be integrated in HEARTS implementation. The objective of this study is to conduct a feasibility and acceptability pilot trial of integrated hypertension and diabetes management based on HEARTS in the publicly funded primary care system in Guatemala.

Methods: A single-arm pilot trial for 6 months will be carried out in 11 Ministry of Health primary care facilities starting in August 2023. A planned sample of 100 adult patients diagnosed with diabetes (n=45), hypertension (n=45), or both (n=10) will be enrolled. The intervention will consist of HEARTS-aligned components: Training health workers on Healthy-lifestyle counseling and Evidence-based treatment protocols; strengthening Access to medications and diagnostics; training on Risk-based cardiovascular disease management; Team-based care and task sharing; and Systems monitoring and feedback, including implementation of a facility-based electronic monitoring tool at the individual level. Co-primary outcomes of feasibility and acceptability will be assessed using quantitative data, qualitative data, and mixed methods. Secondary outcomes include clinical effectiveness (glycemic and blood pressure control), key implementation outcomes (adoption, fidelity, usability, and sustainability), and patient-related outcome measures (diabetes distress, disability, and treatment burden). Using an implementation mapping approach, a Technical Advisory Committee will develop implementation strategies for subsequent scale-up planning.

Discussion: This trial will produce evidence on implementing HEARTS-aligned hypertension and diabetes care in the MOH primary care system in Guatemala. Results also may inform HEARTS implementation efforts in other low- and middle-income countries.

2. ABBREVIATIONS

AEs	Adverse events
AIM	Acceptability of Intervention Measure
APEASE	Acceptability, feasibility, effectiveness, cost-effectiveness, side effects or unintended consequences, safety, and equity
CSAT	Clinical Sustainability Assessment Tool
DBP	Diastolic blood pressure
DDS	Diabetes Distress Scale
DHIS2	District Health Information System 2
FBG	Fasting blood glucose
FIM	Feasibility of Intervention Measure
HbA1c	Hemoglobin A1c
HEARTS	Healthy lifestyle counseling, Evidence-based protocols, Access to medicines, Risk-based management, Team care and task sharing, and Systems monitoring (World Health Organization's model for the primary care management of cardiometabolic diseases)
INCAP	Institute of Nutrition of Central America and Panama
IRB	Institutional review board
LMICs	Low- and middle-income countries
MOH	Ministry of Health
MULTIPIeS	Multimorbidity Illness Perceptions Scale
NIH	National Institutes of Health
ORIO	Other reportable information or occurrence
PAHO	Pan American Health Organization
PI	Principal investigator
PROEDUSA	Department of Health Training and Education
PSAT	Program Sustainability Assessment Tool
REDCap	Research Electronic Data Capture
SBP	Systolic blood pressure
SIAS	Comprehensive Health Care System
SIGSA	Health Management Information System
TAC	Technical Advisory Committee
TICD	Tailored Implementation in Chronic Diseases
WHO	World Health Organization

3. BACKGROUND AND RATIONALE

Approximately 80% of the global burden of hypertension and diabetes occurs in low- and middle-income countries (LMICs).¹ Widespread adoption of evidence-based treatment of these diseases in high-income countries contributes to markedly better outcomes than in LMICs, where adoption is often limited.²⁻⁶ To address this implementation gap, the World Health Organization (WHO) developed the HEARTS Technical Package.⁷ HEARTS is an integrated model for the primary care management of cardiometabolic diseases. The model has six components: Healthy lifestyle counseling, Evidence-based protocols, Access to medicines, Risk-based management, Team care and task sharing, and Systems monitoring. The HEARTS components align with successful multicomponent interventions such as the U.S. Kaiser Permanente hypertension program.⁸ HEARTS was designed to be a flexible platform to improve cardiometabolic care within national primary care systems.

Through its “Hearts in the Americas” initiative, the Pan American Health Organization (PAHO) has spearheaded efforts to implement HEARTS in national health systems throughout the Americas region.⁹ HEARTS implementation projects to date have focused on hypertension as it the highest-burden cardiovascular disease risk factor.¹⁰ To further its impact, HEARTS can be expanded to integrate management of other cardiometabolic diseases such as diabetes.¹¹ The HEARTS-D module primarily focuses on clinical diabetes recommendations. Given the diversity of health systems where HEARTS is implemented, there is thus a need for generalizable evidence on how integrated hypertension and diabetes care can be achieved, scaled, and sustained.¹¹

Guatemala is a middle-income country with the highest burden of cardiometabolic diseases in Central America.¹² An estimated 32.2%⁴ and 13.1%¹³ of Guatemalan adults have hypertension and diabetes, respectively, and the two diseases account for one-quarter of national deaths.¹² This project builds on prior hypertension control projects in Guatemala by study investigators and collaborators in the Ministry of Health (MOH) and PAHO. From 2017-2022, study team members implemented a HEARTS-aligned multicomponent hypertension project across MOH primary care facilities in 5 of the country’s 22 departments.¹⁴⁻¹⁶ In 2021, study team members initiated a HEARTS pilot in 6 MOH primary care facilities. Finally, in November 2022, HEARTS was officially launched by the MOH and PAHO.¹⁷ While HEARTS in Guatemala initially focuses on hypertension, national authorities are interested to exploring how diabetes can be integrated into ongoing implementation efforts. This trial will pilot the Integrated Hypertension and Diabetes Primary Care Model based on HEARTS in the publicly funded primary care system in Guatemala.

4. STUDY OBJECTIVE

The primary objective of this study is to test the feasibility and acceptability of an integrated model hypertension and diabetes management based on HEARTS in the publicly funded primary care system in Guatemala. The terms *feasibility* can refer to different concepts and domains in pilot studies.¹⁸ In this protocol, we use the term specifically in reference to implementation outcomes. Secondary objectives of this study are to rehearse study procedures and to engage with key stakeholders to develop implementation strategies for a subsequent scale-up project.

5. METHODS

This protocol follows SPIRIT guidelines for clinical trial protocols.¹⁹ Guidance on reporting non-randomized pilot studies, conducting pilot implementation studies and applying mixed methods to pilot studies also were applied as appropriate.^{20,21}

5.1. Study design

A single-arm pilot trial over 6 months duration will be carried out in 11 Ministry of Health (MOH)-led primary care facilities. A single-arm design was chosen as most appropriate to evaluate feasibility and acceptability and to align with recommendations for pilot projects in the HEARTS Implementation Guide.²²

5.2. Study setting

5.2.1. *Participating health facilities*

This study will be carried out in 11 MOH primary care facilities in two health districts (**Figure 1**). The two health districts were selected in consultation with the MOH and PAHO. Each health district includes one second-level primary health facility (health center) and referring first-level primary health facilities (health posts). A breakdown of these primary care facilities is shown in **Table 1**. Both health districts were sites where the study team previously implemented HEARTS-aligned hypertension control projects. The two health districts were purposefully selected to represent important areas of diversity in Guatemala across location and ethnicity. Neither health district was part of the initial wave of HEARTS implementation in Guatemala (see 5.1: Context of HEARTS implementation in Guatemala). It was also important that each site had motivated MOH leadership.²² The selected health district in Sololá (San Pablo La Laguna) is located in the Central Highlands and has a primarily indigenous Maya population. The selected health district in Chiquimula (Esquipulas) is located in Eastern Guatemala and has a primarily non-Indigenous population. Both health districts have poverty rates of 60-70%²³ with large rural populations.²⁴

Figure 1: Map of study setting

[figure not shown]

Table 1: MOH primary care sites for implementation

Department (health area)	Health district	Health centers, n	Health posts, n	Location	Population of health district	Ethnic group
Sololá	San Pablo La Laguna	1	5	Central Highlands	88,623	94.5% Maya Indigenous
Chiquimula	Esquipulas	1	4	Eastern Guatemala	55,556	96.3% non-Indigenous
Total		2	9			

5.2.2. Study context

Most poor patients with hypertension and diabetes in Guatemala depend on the Ministry of Health-led system for health care. The MOH system is a national, publicly funded system consisting of multiple levels.²⁵ The first two levels are the primary care levels where this project will be conducted. Primary care in the MOH system is coordinated by the Comprehensive Health Care System (*Sistema Integral de Atención en Salud* [SIAS]), which is a department in the MOH responsible for health service delivery. The National Program for the Prevention of Chronic Non-Communicable Diseases and Cancer coordinates hypertension and diabetes policies in the MOH.²⁶

The first level of the MOH system are health posts. Health posts are located in rural villages, are typically open during business hours on weekdays, and are staffed by 1-2 auxiliary nurses. Auxiliary nurses are full-time MOH employees and have similar training to

nursing assistants in the U.S. health care system. Their scope of practice includes a wide range of basic preventative and curative primary care services, though auxiliary nurses typically do not provide pharmacological management of non-communicable diseases such as diabetes or hypertension.

- The second level of the MOH system are health centers. Health centers are located in urban or semi-urban areas in mid-sized towns, are open 24/7 for emergencies, and are staffed by professional nurses, general physicians, physicians-in-training, or a combination thereof. Professional nurses have similar training to registered nurses in the U.S. health care system, and their scope of practice encompasses that of auxiliary nurses with additional responsibility for more complex patient management. Health centers manage uncomplicated diabetes or hypertension cases. Available resources typically include oral medications and tools for measuring blood glucose and blood pressure.
- The third level of the MOH system are hospitals. Hospitals are located in regional capital cities and in Guatemala City, are open 24/7, and have additional staffing above health centers, including physician specialists. MOH hospitals have both inpatient and outpatient services for complex patients. Patients needing insulin therapy, acute inpatient care, or specialist management of diabetes or hypertension complications are referred to this level of care per the MOH protocols describe below.

Clinical guidelines. The MOH regularly releases clinical guidelines for primary care clinicians in Guatemala. The most recent hypertension and diabetes guidelines were released in 2018, were updated in 2023,²⁷ and are generally consistent with international guidelines.²⁸ The main challenge relating to clinical guidelines in Guatemala is the need for investments to support guideline implementation, including staffing, training and supervision, and equipping primary care facilities with clinical resources.

Clinical data systems. At present, there is no standardized paper or electronic patient medical record in the MOH-led health system. As a result, there is difficulty tracking individual patients over time or between health system levels. There is also no official diabetes or hypertension registry. The MOH has an electronic tool, the Health Management Information System, that is primarily used to monitor patient volume and to manage staffing needs (*Sistema de Información Gerencial de Salud [SIGSA]*). However, the SIGSA system is not designed to capture longitudinal patient data, and thus clinicians cannot use the system to provide clinical care with information from prior encounters with the health system.

Availability and cost of medications and diagnostics. Guatemalan laws guarantee that health care is free of charge at MOH health facilities.²⁵ The MOH thus is responsible for ensuring the availability of quality medications and supplies relating to hypertension and diabetes. At the primary care level, the most commonly available medications for hypertension are hydrochlorothiazide, enalapril, and losartan; the most commonly available medications for diabetes are metformin and glimepiride. Tests such as hemoglobin A1c (HbA1c), creatinine, or cholesterol are not available at MOH-led primary care facilities, though patients sometimes present results obtained at private laboratory facilities. Stockouts of medications and diagnostics commonly occur.²⁹

Context of HEARTS implementation in Guatemala. In November 2022, with support from PAHO, the Guatemalan MOH committed to participate in the “Hearts in the Americas” initiative.¹⁷ The MOH plans a stepped implementation of HEARTS across the country. The first 36 health districts across 6 of 22 departments in the country were enrolled in late 2022 and

2023. (“Departments” are first-level political subdivisions in Guatemala and are analogous to U.S. states.; each department has an corresponding administrative “health area” in the MOH system.) As noted above, neither of the sites in this pilot were included in the initial wave of HEARTS implementation in Guatemala. The MOH has committed resources to HEARTS, in particular to improve access to medications and supplies. To date, HEARTS implementation in Guatemala has focused only on hypertension management at MOH health centers. Diabetes management is not currently part of the MOH’s HEARTS strategy.

5.3. Participant eligibility criteria

5.3.1. *Patient participants*

Inclusion criteria: All non-pregnant adults aged ≥ 18 years with diagnoses of type 2 diabetes, hypertension, or both conditions who present for routine care at participating MOH primary health facilities between over a 6-month period will be included (“patient participants”).

Both previously diagnosed and newly diagnosed patients will be eligible. Previously diagnosed patients will be identified by MOH primary care clinicians who take medical histories as part of routine care. Newly diagnosed patients will be identified by MOH primary care clinicians who apply hypertension and diabetes diagnostic criteria from national guidelines.^{27,28}

- Diabetes diagnostic criteria for newly diagnosed patients: fasting glucose ≥ 126 mg/dl, two-hour post-prandial glucose ≥ 200 mg/dl, HbA1c $\geq 6.5\%$.
- Hypertension diagnostic criteria for newly diagnosed patients: include systolic blood pressure ≥ 130 mmHg or diastolic blood pressure ≥ 80 mmHg. A new hypertension diagnosis must be based on the average of at least two measurements performed on two separate occasions.

Exclusion criteria: Participants with confirmed or suspected type 1 diabetes or who are pregnant will be excluded, as these patients are not managed at MOH health centers or health posts. Participants with a prior history of cardiovascular disease will not be excluded.

[figure not shown]
5.3.2. *Other participants*

All MOH staff (physicians, nurses, auxiliary nurses) and stakeholders on the Technical Advisory Committee will be eligible for participation in the implementation assessment of the pilot (“MOH participants”). Details on the Technical Advisory Committee members are provided in 7.3.5.

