6. OUTCOMES

6.1. Primary outcomes

Primary outcomes will be feasibility and acceptability as defined in the Implementation Outcomes Framework (**Table 2**).³⁸ These outcomes will be assessed using quantitative data, qualitative data, and mixed methods (integrated qualitative and quantitative data). Given the study team's prior experience with HEARTS-aligned projects, the focus of the feasibility and acceptability assessments will be on integrating diabetes into the HEARTS model.

Feasibility is the extent to which a new intervention can be successfully carried out in an organization.³⁸ Among MOH participants, feasibility will be assessed through the four-item Feasibility of Intervention Measure (FIM) questionnaire³⁹ and semi-structured interviews. Among patient participants, feasibility will be assessed using enrollment data.

Acceptability is the stakeholders' perception that a new intervention is agreeable or satisfactory.³⁸ Among MOH participants, acceptability will be assessed using the Acceptability of Intervention Measure (AIM) questionnaire³⁹ and semi-structured interviews. Among patient participants, acceptability will be assessed using follow-up visit data and semi-structured interviews.

Table 2: Measures of feasibility and acceptability and their benchmarks

Measure	Minimum benchmark
Feasibility	
Feasibility questionnaire (FIM) among MOH participants	Median $\geq 3.5^a$
Reasons for perceptions of feasibility/infeasibility	N/A
Number of patient participants with diabetes enrolled per health district ^b	25
Number of patient participants with hypertension enrolled per health district ^b	25
Acceptability	
Acceptability questionnaire (AIM) among MOH participants	Median $\geq 3.5^a$

Table 2: Measures of feasibility and acceptability and their benchmarks

Measure	Minimum benchmark
Proportion of patient participants with subsequent follow-up visit within 3 months (among those enrolled with ≥ 3 months remaining in pilot)	75%
Reasons for perceptions of acceptability/infeasibility among patient and MOH participants	N/A
Reasons for dropouts among patient participants	N/A

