7.2. Recruitment and sampling

[figure not shown]
This project is embedded in MOH-led standard routine primary care services. All new or existing patients with diabetes or hypertension receiving care at the participating MOH primary care facilities will be enrolled in the DHIS2 system. Recruitment activities will be carried out that align with the routine outreach activities of each MOH health facility; these activities may include

meetings with local leaders, public posters, and brief announcements on social media platforms or the radio.

A subset of patient participants (n=10, of whom n=5 from each health district) will be recruited for questionnaire assessments and interviews. These patient participants will be purposively selected among individuals who had enrolled in the first two months of the study and had high versus low numbers of patient visits (i.e., explanatory sequential mixed methods sampling). Study fieldworkers who are not MOH employees will make an initial contact via home visit, phone calls, or encounters at MOH health facilities. Participants who express interest in this part of the study will then receive a visit by study fieldworkers to complete informed consent and interview assessments. This visit will occur in the patient's home or another convenient private location, depending on the patient's preference.

All MOH participants and members of the Technical Advisory Committee will be asked to complete a structured questionnaire. The study team will use lists of personnel participating in trainings and contacts at each health district to identify MOH participants. Members of the Technical Advisory Committee will be recruited using INCAPs local contacts and connections from prior projects with the MOH. Subsequently, a subsample of approximately 20 MOH participants will be purposively selected for semi-structured interviews based on high versus low perceptions of intervention feasibility (i.e., explanatory sequential mixed methods sampling). Mixed-methods procedural diagrams are shown in **Figure 4**.

Figure 4: Mixed-methods procedural diagram

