7.3.4. Closing interviews with MOH health workers and administrators

All MOH participants participating in the pilot will be invited to complete a structured questionnaire, focusing on feasibility (FIM instrument), sustainability (PSAT/CSAT instrument), and usability of the facility-based electronic monitoring tool (System Usability Scale). Additionally, a subsample of approximately 20 MOH staff will be purposely selected to participate in semi-structured interviews lasting approximately 45 minutes. The TICD checklist will guide the semi-structured interviews.⁵³ Interviews may be conducted in-person or virtually.

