15. SUPPLEMENTARY FILES

The following supplementary files are included with this protocol.

1. Spirit checklist
2. DHIS2 visit forms
3. Baseline health facility assessments
4. Follow-up health facility assessments
5. Chart audit form
6. Technical Advisory Committee meetings agenda and discussion prompts
7. Structured questionnaire and semi-structured interview guide for patient participants
8. Structured questionnaire for MOH participants
9. Semi-structured interview guide for MOH participants
10. Consent form: Patient and MOH participants who are interviewed
11. Consent form: Technical Advisory Committee members
12. Patient participant handout at primary health facilities
13. Poster at health facilities

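### Does it matter that Technical Advisory Committee members are counted as MOH participants in section 5.3.2 but listed apart from them in section 7.2?

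*Combined protocol and SAP*

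**What the plan says.** The label is defined once, in section 5.3.2: "All MOH staff (physicians, nurses, auxiliary nurses) and stakeholders on the Technical Advisory Committee will be eligible for participation" in the implementation assessment, and the sentence names that combined group MOH participants. Table 2 in section 6.1 then lists "Feasibility questionnaire (FIM) among MOH participants" and "Acceptability questionnaire (AIM) among MOH participants", each with a minimum benchmark of a median of at least 3.5 on a 1-to-5 scale.

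Section 7.2 treats the two as different groups: "All MOH participants and members of the Technical Advisory Committee will be asked to complete a structured questionnaire". It finds MOH participants through training lists and district contacts, and TAC members through INCAP's own contacts. Section 7.3.4, headed for health workers and administrators, says "All MOH participants participating in the pilot will be invited to complete a structured questionnaire" and lists FIM in it, without mentioning the TAC. Section 8 expects about 50 MOH participants engaged in implementing HEARTS. Section 7.3.5 puts the TAC at 10 to 15 people, likely to include district clinicians, administrators up to national level and PAHO representatives. Section 9 says that questionnaires are summarized descriptively and names no analysis set.

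**The concern.** Read literally, section 5.3.2 brings TAC scores into both medians. Read through section 7.2, they stay out. Nothing in the visible text settles which applies, whether the approximate 50 includes the TAC, or how a district clinician who also sits on the TAC is counted.

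FIM and AIM are the only questionnaire benchmarks for the co-primary outcomes. Section 6.1 says "Feasibility is the extent to which a new intervention can be successfully carried out in an organization", and some TAC members do not deliver care in the 11 facilities, while section 7.3.5 gives the committee a part in designing implementation strategies. If the choice were made after the scores were seen, it could decide a close result in either direction.

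**Working it through.** The plan gives no figure on this point to reproduce. Two checks apply: how the label is used, and how far pooling could move a median.

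**Use of the label**

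- Section 5.3.2: staff plus TAC.
- Section 7.2: two groups, two identification routes.
- Section 7.3.4: FIM goes to those taking part in the pilot, under a heading for health workers and administrators.
- Section 8: about 50 people implementing HEARTS.
- Section 11.3: participants are patients and the MOH staff who provide or supervise care.
- Section 11.4: MOH participants receive clinical training, which does not describe PAHO representatives.
- Section 11.5.2: the consent script ties MOH participants to their employment, and TAC stakeholders are named separately from interviewees.
- Section 12: MOH participants hear results at district meetings; the TAC is a further channel for MOH stakeholders.

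Section 5.3.2 is the outlier.

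**Does the TAC complete FIM and AIM?** Section 15 lists one questionnaire for patients and one titled "Structured questionnaire for MOH participants". The TAC has a consent form and "Technical Advisory Committee meetings agenda and discussion prompts". By elimination the TAC may receive the MOH form, but its content is not visible, so this is an inference.

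**Effect of pooling.** Inputs: 50 staff respond (section 8, assumed to exclude the TAC); *b* of them score below 3.5; *k* TAC members who are not already counted as staff are added (*k* is not in the documents).

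Staff alone: the median is the mean of the 25th and 26th ordered scores. It meets 3.5 for certain if b ≤ 24 and misses for certain if b ≥ 26. At b = 25 it depends on the two middle values.

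The extreme cases put all *k* scores on one side of 3.5. For odd *k* the pooled median is the score at rank (51 + k)/2:

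- k = 3, rank 27. All at or above 3.5: met if b ≤ 26. All below: met if b + 3 ≤ 26, so b ≤ 23.
- k = 5, rank 28. All at or above: met if b ≤ 27. All below: met if b + 5 ≤ 27, so b ≤ 22.
- k = 15, rank 33. All at or above: met if b ≤ 32. All below: met if b + 15 ≤ 32, so b ≤ 17.

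For k = 10 the two middle ranks are 30 and 31: met for certain if b ≤ 29 (all at or above), missed for certain if b + 10 ≥ 31, so b ≥ 21 (all below).

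| k | missed becomes met | met becomes missed |
|---|---|---|
| 1 or 2 | none for certain | none for certain |
| 3 | b = 26 | b = 24 |
| 5 | b = 26, 27 | b = 23, 24 |
| 10 | b = 26 to 29 | b = 21 to 24 |
| 15 | b = 26 to 32 | b = 18 to 24 |

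With 40 staff and k = 5, the certain reversals are b = 21, 22 and b = 18, 19.

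**In score points.** If all TAC scores lie above all staff scores, the pooled median is the staff score at percentile p = rank/(50 + 1). For k = 10, p = 30.5/51 = 0.598; for k = 15, p = 33/51 = 0.647. Taking staff scores as normal with an assumed SD of 0.5 to 1.0, the largest shift, SD × z(p), is 0.12 to 0.25 points for k = 10 and 0.19 to 0.38 for k = 15. If 15 TAC members sit inside the 50, leaving 35 staff, p = 25.5/36 = 0.708 and the bound is 0.27 to 0.55.

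**How often it would matter.** A simulation used 50 staff, 10 or 15 TAC members, SD 0.75, and TAC means 0.5 below, 0.5 above or 1.0 above staff (all assumed apart from the group sizes). The result against 3.5 changed in about 5% to 60% of runs for staff means of 3.25 to 3.6, in at most 8% at 3.0, in about 1% or fewer at 3.75, and in none at 2.75, 4.0 or 4.25.

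**The case for a change.** The strongest case for a change is that section 5.3.2 holds the only formal definition, so an analyst who follows it is not misreading the plan, and the set behind two co-primary benchmarks should not be open once scores are known. TAC members with no facility role might also rate the model differently from those who run it. Naming the set would take a few sentences.

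Part of this stands. The sections do conflict, and a close result could turn on the reading. With all 10 to 15 TAC members added, the exposed splits are not trivially narrow, although overlap with district staff makes the full number unlikely.

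Three things limit it. First, the effect needs the TAC to complete FIM and AIM, which is only inferred. Second, missing a benchmark triggers nothing in the plan: section 9 reads the medians beside the interviews in joint displays, and section 10.2 bases any extension on funding and judgement. Third, removing the TAC from both medians is not clearly better. Section 6.1 defines acceptability by what stakeholders think, section 5.3.2 calls TAC members stakeholders, and section 5.4.5 makes departmental officials recipients of the monthly reports, which are one of the five components. Some TAC members therefore have a proper claim to be heard on these scales.

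**Conclusion.** The inconsistency is a drafting slip in an eligibility sentence, and it leaves a gap that analysts can fill sensibly from the rest of the protocol: staff form the FIM and AIM medians, dual-role members count once, and any TAC scores are shown alongside. Staff roles must already be known, because Table 4 draws the interview sample by role, and the TAC is a short list with its own consent form, so the two can be described separately without new data.

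No change to the plan is called for. The exposure is limited to staff splits near half: 23 to 27 of 50 below 3.5 for five added scores, and at most 18 to 32 for fifteen, in each case with all added scores on one side (at 25 of 50 the staff-only result itself depends on the two middle scores). Enrollment counts, the 75% follow-up measure and the interviews are unaffected. These sizes assume 50 staff respondents, TAC members additional to them, and a TAC that completes both scales. The documents do not give the number added, the SDs or the gap between staff and TAC scores.
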